5.3.4 Timelines for reporting

After informed consent has been obtained and after initiation of study related interventions:

All AEs and SAEs causally related to a study-related intervention and AESIs will be reported until 30 days after the last study-related intervention or until last follow-up visit (whichever occurs first).

All SARs and AESI as defined in the protocol must be reported to the Sponsor within 24 hours of the study staff becoming aware of the event. The immediate report shall be followed by detailed, written reports. The immediate and follow-up reports shall identify participants by study pseudonym.

SAR details will be reported by the Investigator to the Sponsor:

- By completing the SAE form in the eCRF
- By completing a paper SAE form and sending it to the following address in the event of a technical malfunction or if the eCRF does not have built-in notifications:

Mail: [contact]

5.3.5 Follow-up

The Investigator must record follow-up information by updating the participant's medical records and the appropriate forms in the eCRF. A change in parameters (severity, seriousness, etc,) of the event will be recorded as a separate event .

SAE follow-up information should only include new (e.g. corrections or additional) information and must be reported within 24 hours of the Investigator's first knowledge of the information. This is also the case for previously non-serious AEs which subsequently become SAEs.

- All SAEs must be followed up until the outcome of the event is either 'recovered', 'recovered with sequelae', 'not recovered' (in case of death due to another cause) or 'death' (due to the SAE) and until all related queries have been resolved, or until end of study (whichever occurs first).
- Non-serious AEs must be followed up until the participant's last study visit, and until all related queries have been resolved.

SAEs after the end of the study: If the Investigator becomes aware of an SAE with suspected causal relationship to the study intervention or study participation after the participant has ended the study, the Investigator should report this SAE within the same timelines as for SAEs during the study.

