2.5 Expected duration of the study

Expected overall study duration for the research site

We expect the overall study duration to be **one year**. UZ Leuven currently follows 274 patients with left bundle branch area (LBBA) pacing, while Jessa Hospital follows 400 patients. Since our goal is to include 20 patients, approximately 3% of all LBB area pacing patients will need to consent to participate in the study. This percentage will be even higher after excluding patients who do not meet the eligibility criteria. Therefore, to achieve our target sample size of 20 patients, we anticipate needing to approach nearly all eligible LBB area pacing patients who attend their regular (at least) **annual** pacemaker or heart failure consultation. After screening at their annual pacemaker consultation, the study visit can be planned within three weeks.

Expected overall study duration for a single participant

For individual participants, the study duration is expected to be less than three weeks. After providing informed consent, the study visit can be scheduled within this timeframe. The total study visit is expected to take 2 hours. After the study visit, the study ends.

The End of Study (EoS) is defined as Last Participant Last Visit (LPLV). The Sponsor-Investigator shall notify the EC of the end of the study. The Sponsor-Investigator will submit a final report with the results of the study, including any publications/abstracts, to the Competent Authorities (CA)/Ethics Committee (EC) within 1 year of study termination or within 6 months for paediatric studies.

The Sponsor or EC can decide to halt or prematurely terminate the study when new information becomes available whereby the rights, safety and well-being of study participants can no longer be assured, when the integrity of the study has been compromised, or when the scientific value of the study becomes obsolete and/or unjustifiable.

Circumstances requiring premature treatment interruption or discontinuation of the study, include but are not limited to:

- Safety concerns or unacceptable intolerability

Should the study be temporarily suspended or, ended prematurely, the Sponsor-Investigator will notify the EC and include the reasons for suspension/premature termination within 15 days of the decision.

3 Study population / Eligibility criteria

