5.1.5 Adverse Events of Special Interest (AESI)

The following events should be reported within the same timelines as SAEs:

- Adverse events related during iCPET
 - ECG signifying myocardial injury
 - ECG signifying current or potentially lethal arrhythmias
 - Systemic hypotension (e.g. systolic blood pressure < 90 mmHg)
 - Extreme hypertension (e.g. systolic blood pressure > 220 mmHg)
 - Syncope, presyncope, or lightheadedness
 - SaO₂ < 88%
 - Severely elevated PCWP (> 40 mmHg) during exercise
- Adverse events related to jugular catheter insertion and PCWP-measurement
 - Air embolism
 - Pulmonary artery perforation
 - Infection
 - Pneumothorax
 - Arrhythmias
 - Hypotension
- Adverse events related to arterial catheter insertion
 - Permanent vessel occlusion
 - Pseudoaneurysm formation
 - Infection
 - Air embolism

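### No contact is planned after the iCPET, so non-serious events and non-serious AESIs are not followed beyond that visit, and SAE follow-up is capped at last participant last visit

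*Combined protocol and SAP*

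**What the plan says.** **Non-serious events.** Section 5.3.5 (Follow-up): "Non-serious AEs must be followed up until the participant's last study visit, and until all related queries have been resolved". In both flowcharts the last visit is the iCPET visit, and it is the only one marked for adverse event assessment. Section 2.5, on the duration for a single participant, says "After the study visit, the study ends". The end-of-study-phase text in section 4.2.2 gives 15 minutes of vital-sign monitoring after the procedure.

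**SAEs.** Section 5.3.5 requires follow-up to a defined outcome and until queries are resolved, "or until end of study (whichever occurs first". Section 2.5: "The End of Study (EoS) is defined as Last Participant Last Visit (LPLV".

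**Reporting window.** Under section 5.3.4, related AEs, related SAEs and AESIs "will be reported until 30 days after the last study-related intervention or until last follow-up visit (whichever occurs first".

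**AESIs.** Section 5.1.5 gives AESIs the SAE reporting timelines. Neither it nor section 5.3.5 gives them a follow-up rule. The list includes "Permanent vessel occlusion", pseudoaneurysm and infection. The risk assessment in section 1 names temporary occlusion as well, but only the permanent form is an AESI.

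**Data required.** Section 5.3.1 makes stop date and outcome part of the minimum record for each adverse reaction, serious or not.

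**The concern.** How long a known event is followed is a separate question from how long new events are reported, and here the two rules do not fit the visit schedule or each other.

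Whether an occlusion is permanent can only be judged over time. Pseudoaneurysm and infection need not show themselves within 15 minutes of catheter removal. The plan has no contact after that point, no time criterion for permanent and no scheduled check. Section 5.3.5 itself expects that some non-serious events will later become serious, but it provides no follow-up in which that would be seen.

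At stake is the completeness of the safety record of an invasive study: required outcome fields left open, AESIs missed or misclassified, and a maximum SAE follow-up that depends on the order of enrolment rather than on the event.

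**Working it through.** The plan gives no figure for length of follow-up, so there is none to reproduce. The check sets the rules side by side and then does the date arithmetic.

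**1. Non-serious AEs and AESIs.** Limit: the participant's last study visit (5.3.5). Last visit: the iCPET (flowcharts, 2.5). Planned follow-up after that day: 0 days for all 20 participants. The query clause may keep a record open but schedules no contact.

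**2. Reporting window.** There are two ways to read the last follow-up visit in section 5.3.4.
- It is the iCPET visit. Reporting then closes that day and the 30 days never apply.
- There is no such visit. The window is then 30 days, but section 5.3.1 seeks events at participant contacts and none is planned. A non-serious event that came to light on, say, day 5 would be reportable although its follow-up had already closed.

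**3. SAEs.** Inputs from the synopsis: first visit 01/10/2025, LPLV 30/09/2026, 20 participants. The span is 364 days. The accrual pattern is not stated, so two are assumed.

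| Assumed pattern | Spacing | Days from visit to LPLV (min / median / max) | Participants under 30 days |
|---|---|---|---|
| Even, study visits from day 0 | 364/19 = 19.2 days | 0 / 182 / 364 | 2 of 20 |
| Even, first study visit on day 21 (the three-week interval in 2.5) | 343/19 = 18.1 days | 0 / 171.5 / 343 | 2 of 20 |
| Random uniform, LPLV set by the latest visit | – | – | mean 2.6, 5th–95th percentile 1 to 5 |

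In the even patterns the last participant has 0 days and the one before has 18 to 19; the next already has 36 to 38. For the random pattern, the mean is 1 + 20 × 30/364 = 2.65, which agrees with 200,000 simulated trials.

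**4. Chance that a serious event falls where follow-up is cut.** Section 1 cites a serious event rate of 1.1% for right heart catheterization.
- Any such event in 20 procedures: 1 − 0.989^20 = 19.8%.
- In the 2 participants with under 30 days: 1 − 0.989^2 = 2.2%.
- In 1 to 5 participants: 1.1% to 1 − 0.989^5 = 5.4%.

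Only the last two lines bear on shortened SAE follow-up. The protocol gives no rate for radial occlusion.

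**The case against.** Much of the opposing case is sound.

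- **SAEs are followed to outcome.** A reader might infer that no event has follow-up to outcome. Section 5.3.5 says otherwise for SAEs, and under even accrual about 18 of 20 participants have at least 30 days before LPLV. This stands. A reader might also apply the sentence that the study ends after the visit to SAEs, which would stop follow-up on the iCPET day for everyone. The defined term is LPLV, so the text does not support that.
- **The 30 days are not unconditional.** If the window closes at the iCPET visit, reporting and non-serious follow-up end together and do not conflict. This stands as a reading, but it makes the 30 days empty and leaves later non-serious events unreported.
- **Queries and written reports.** Non-serious follow-up also runs until queries are resolved, and section 5.3.4 requires detailed written reports after the immediate report of a serious reaction or AESI. Both can lengthen follow-up of an event already recorded. Neither schedules a contact, and section 7.3 waives independent monitoring.
- **Post-study clause and routine care.** Related SAEs learned of after the participant has ended the study must be reported, and participants stay under at least annual consultation (section 4.1). Both routes are passive. The clause covers reporting of SAEs only, not follow-up to outcome and not non-serious AESIs.
- **Permanent occlusion could still be established.** It could if the occlusion met a seriousness criterion, or if routine care found it. To say that it can never be established goes too far.
- **Limited consequence.** No objective, endpoint or planned analysis concerns access-site safety. This stands.

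**Conclusion.** The point holds in a limited form. For non-serious AEs, and by default non-serious AESIs, planned follow-up after the iCPET visit is zero for all 20 participants; this follows from the text alone. Permanent occlusion, pseudoaneurysm and infection that do not meet an SAE criterion therefore cannot be reliably identified or followed to outcome from planned study data. The 30-day window in section 5.3.4 either never operates or has no means of collection.

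For SAEs the defect is small: under 30 days of available follow-up for about 2 of 20 participants with even accrual and about 1 to 5 with random accrual, both assumptions. A reader might take the 19.8% as the chance of a truncated serious event. It is the chance of any serious catheterization event in 20 procedures; for 2 affected participants the figure is about 2.2%.

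The primary and secondary results are not affected. This is an inexpensive improvement to safety capture.

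**What to change.** Reconcile sections 2.5, 5.1.5, 5.3.4 and 5.3.5:

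- In 5.3.4, remove the limit at the last follow-up visit or align it with the schedule, and say how events within the 30 days will be collected.
- In 5.3.5, give AESIs an explicit follow-up rule. Follow reported related AEs, AESIs and SAEs to outcome, or at least to the end of the protocol's own 30-day window, independent of LPLV.
- In 5.1.5, state how an occlusion is to be classed as permanent; the criterion is for the sponsor to set.
- In 2.5 and 5.3.5, make clear that end of study means LPLV and not the end of the individual's visit. Moving the end-of-study definition is optional.

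The cost is about one paragraph of amendment, a call or routine-care record check for the few participants with an open event, and up to 30 days before the safety data close.

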5.3.6 Pregnancy

Female participants must be instructed to notify the Investigator immediately if they become pregnant during the Study. The Investigator must report any pregnancy to the Sponsor.

5.3.7 Death

Deaths of subjects who were participating in the study at the time of their death will be reported to the Sponsor without delay (irrespective of whether the death is related to disease progression, study procedure or is an unrelated event). The Sponsor will notify all deaths, as soon as possible after becoming aware, to the Central EC. Additionally, deaths occurring at a specific site will be reported to the EC of the concerned site, if requested by the respective EC.

5.4 Reporting requirements to Ethics Committee's (EC's)

The Investigator is responsible for ensuring that all safety events are recorded in the eCRF and reported to the Sponsor in accordance with instructions provided below.

The Sponsor will promptly evaluate all SARs and AESIs against medical experience to identify and expeditiously communicate possible new safety findings to the Investigators and to the EC(s) based on applicable legislation.

6.4.1 Annual reporting

The Sponsor has the obligation to, once a year throughout the study (or on request), submit a progress report to the ECs containing an overview of all SARs that occurred during the reporting period and taking into account all new available safety information received during the reporting period.

5.4.2 Overview reporting requirements

	WHAT	HOW	TO	TIMELINES
Investigator	AR	AE form in eCRF	Sponsor	In a timely manner
	SAR	SAE form in eCRF	Sponsor	Immediately (within 24 hours of becoming aware of the event) Exceptions: as defined in protocol
	death	SAE form in eCRF	Sponsor	asap
Sponsor	death	SAE form + narrative	ECs	asap
	Annual Progress Report	APR template	ECs	annually

5.4.3 Pharmacovigilance / Materiovigilance

Any incidents related to the use of a medical device should be reported to the Competent Authorities according to the materiovigilance guidelines.

6 Statistics and data analysis

A study-specific Statistical Analysis Plan (SAP) will be developed by the Sponsor, to supplement the information below with further details.

6.1 Sample size determination

The sample size calculation is based on the expected difference in PCWP between pacing conditions. A power analysis determined that 16 participants are required to achieve a power of 80% and a significance level of 5% (two-sided), assuming a mean difference of -2 mmHg and a standard deviation of 2.5 mmHg. To account for potential dropout, the study will enroll 20 participants.

6.2 Statistical analysis

This is a prospective, single-arm, multicentre, interventional study in which each patient serves as their own control:

- A two-sided significance level of 0.05 will be used for all statistical tests.
- Data will be analyzed using Python, SPSS and Stata statistical software.
- Descriptive statistics of baseline variables will be used to summarize baseline characteristics.
 - Categorical variables will be presented as number and percentage.
 - Continuous variables will be presented as mean \pm standard deviation or median with interquartile range, depending on the Shapiro-Wilk test for normality.
- Comparison of hemodynamic parameters (PCWP, CO, SV, peripheral oxygen extraction) and SVV will be performed using paired student t-test or Wilcoxon-Mann Whitney test whichever will be appropriate.
- Pearson's or Spearman's correlation coefficients, whichever will be appropriate, will be computed to assess the relationship between changes in PCWP and changes in SVV

Endpoint	Statistical analysis methods
Primary	paired student t-test or Wilcoxon-Mann Whitney test
Secondary	paired student t-test or Wilcoxon-Mann Whitney test
Exploratory	descriptive statistics, Pearson's or Spearman's correlation coefficient

7 Data handling

A study-specific Data Management Plan (DMP) will be developed by the Sponsor providing a.o. further details on data flows, data handling, processing and discrepancy management.

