This study aims to assess the impact of accelerated pacing with tailored AV-regulation on the PCWP during exercise in patients with HFpEF, particularly at lower intensities of exertion, which are most relevant for daily activities. By determining whether accelerated pacing improves PCWP during exertion, we aim to provide insights into novel pacing-based interventions that could enhance exercise tolerance and ultimately improve quality of life in patients with HFpEF.

Risk assessment

When performed in experienced centers, right heart catheterization (RHC) is generally considered a safe procedure with low morbidity and mortality rates. A comprehensive analysis of 7,218 procedures, including both retrospective (5,727 cases) and prospective (1,491 cases) data, found an overall serious adverse event rate of 1.1% (95% CI: 0.8%–1.3%). The most frequent complications were related to venous access, such as hematoma and pneumothorax, followed by arrhythmias and hypotensive episodes due to vagal reactions or pulmonary vasoreactivity testing. The vast majority of these complications were mild to moderate in intensity and resolved spontaneously or with appropriate intervention (29). More severe complications are rare. Complete heart block or air embolism can lead to chest pain, shortness of breath, and hypotension. Pulmonary artery perforation, seen in approximately 0.03% of cases, may cause sudden respiratory distress and cardiogenic shock. In these cases, complications may require advanced medical intervention (30).

Radial artery canalization is generally well tolerated; complications are uncommon and include, but are not exclusive to, temporary or permanent vessel occlusion, pseudoaneurysm formation, infection, and, rarely, air embolism. Local pain at the site of cannulation, however, is common and may persist for days (31).

Potential complications of CPET include fatigue, leg pain and shortness of breath. Less common complications include cardiac arrhythmias, anginal chest pain, and bronchospasm. Additionally, CPET may lead to hypotension, occasional premature ventricular contractions (PVCs), and, in rare cases, significant ST-segment depression, which typically resolve after test termination. Overall, CPET remains a safe procedure with a low incidence of complications when conducted under medical supervision (32, 33).

2 Study objectives & design

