2.1 Study objectives

In this study, we plan to address the impact of accelerated pacing with AV-regulation on the PCWP at rest and during exercise in patients with HFpEF. We hypothesize that accelerated pacing with AV-delay regulation reduces PCWP at rest and during exercise up to an optimal pacing rate beyond which no further benefit is observed.

In this study, we aim to:

- Evaluate the effect of accelerated pacing with AV-optimization on PCWP at rest.
- Investigate the impact of accelerated pacing with dynamic AV delay programming, while avoiding truncation, on PCWP during exercise at two distinct (low) intensities (10 and 25 Watts) using a semi-supine cycle ergometer.
- Assess the change in CO, SV and peripheral oxygen extraction at the pacing frequency corresponding to the lowest PCWP compared to the intrinsic heart rate. This approach allows examination not only of the effects of pacing on backward cardiac function (as reflected by PCWP), but also on forward cardiac function. By doing so, it excludes the possibility that a reduction in PCWP is merely due to a decreased CO.
- Evaluate the effects of different pacing frequencies on SWV as a non-invasive marker of myocardial stiffness

Ultimately, we aim to offer insights into novel pacing-based interventions to enhance exercise tolerance and quality of life in patients with HFpEF.

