2.2 Primary endpoints

The primary endpoints are:

- The change in PCWP at each pacing frequency (+20 bpm, +40 bpm, +60 bpm) with its corresponding optimal AV delay at rest, compared to PCWP at the intrinsic heart rate.
- The change in PCWP at each pacing frequency (+10 bpm, +30 bpm, +50 bpm) using dynamic AV delay programming, while avoiding truncation, compared to PCWP at the intrinsic heart rate during exercise (cycle ergometry at 10 and 25 Watts)

The PCWP at the intrinsic heart rate is defined as the average of the PCWP at the intrinsic heart rate heart rate before and after each pacing step.

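### Nine PCWP changes are primary and each is tested at 0.05 with no lead comparison, order or success rule, while the sample size covers one unnamed comparison

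*Combined protocol and SAP*

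**What the plan says.** Section 2.2 has two primary endpoints, each covering several comparisons with the intrinsic rate. At rest it is "The change in PCWP at each pacing frequency (+20 bpm, +40 bpm, +60 bpm) with its corresponding optimal AV delay at rest". In exercise it is "The change in PCWP at each pacing frequency (+10 bpm, +30 bpm, +50 bpm) using dynamic AV delay programming", at both 10 and 25 W. The synopsis matches.

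Section 6.2 sets the error rate in one line: "A two-sided significance level of 0.05 will be used for all statistical tests". It assigns a paired t-test or a Wilcoxon-Mann Whitney test to the primary endpoint. It does not say which comparison leads, in what order they are tested, whether any adjustment is made, or how many must succeed.

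Section 6.1 states that "The sample size calculation is based on the expected difference in PCWP between pacing conditions". Its inputs are 80% power at a two-sided 5% level, with the effect given as follows: "assuming a mean difference of -2 mmHg and a standard deviation of 2.5 mmHg". The result is 16 evaluable participants, raised to 20 for dropout. No rate or workload is named.

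Section 2.1 hypothesises a fall in PCWP "up to an optimal pacing rate beyond which no further benefit is observed". Section 6 opens by promising a separate SAP with further detail; that SAP is not among the documents.

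**The concern.** A primary endpoint tested at 5% normally carries a 5% risk of a wrong positive conclusion. Here nine results share the primary label and each gets the full 5%, so the risk for the set is higher. How much higher matters less than the missing rule: the plan does not say whether one significant result of nine makes the study positive, or whether all nine are needed, or something in between. The stated 5% and 80% describe neither extreme.

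The study is single-arm and unblinded, and staff see PCWP at the bedside because Appendix 3 has them choose the final pacing rate from it. A lead comparison named after the results are known would carry little weight. A reader also cannot tell which of the nine results the 20 participants were meant to support.

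**Working it through.** **Count.** Rest: 3 rates. Exercise: 3 rates × 2 workloads = 6. Total: 3 + 6 = 9 primary comparisons.

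**Reproducing the plan's figure.** Inputs from section 6.1: difference 2 mmHg, SD 2.5 mmHg, two-sided 0.05, power 80%. I take 2.5 mmHg as the SD of the paired change. For a paired t-test on n participants, the noncentrality is (2/2.5)√n = 0.8√n on n − 1 degrees of freedom.

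| n evaluable | noncentrality | power |
|---|---|---|
| 14 | 2.99 | 79.0% |
| 15 | 3.10 | 82.1% |
| 16 | 3.20 | 84.8% |
| 20 | 3.58 | 92.4% |

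The smallest n reaching 80% is 15, so the stated 16 is reproduced to within one participant. A dropout of 20% (implied, not stated) gives 16/0.8 = 20. The arithmetic is sound for one comparison at 0.05.

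**Error rate for the set, no effect at any rate.** If the nine tests were independent:
- any false positive: 1 − 0.95⁹ = 0.370
- any false reduction (2.5% each): 1 − 0.975⁹ = 0.204

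The nine changes are not independent. They come from the same patients, and within a condition neighbouring steps share a pacing-off baseline, because each comparator averages the periods before and after the step. The documents give no correlation, so I assumed a common value and simulated nine paired t-tests (40,000 trials, n = 16 and n = 20):

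| assumed correlation | any false reduction | any false positive |
|---|---|---|
| 0 | about 20% | about 37% |
| 0.5 | about 14% | about 28% |
| 0.9 | 6-7% | about 13% |

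**The opposite rule.** If all nine had to be significant and the true change were −2 mmHg (SD 2.5) everywhere, power at n = 16 would be about 23%, 47% or 71% for correlations 0, 0.5 and 0.9.

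**Can a lead be inferred?** The study rationale stresses exercise, "particularly at lower intensities of exertion, which are most relevant for daily activities". That removes rest but leaves six comparisons, and section 2.2 gives rest and exercise equal standing.

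**What a lead with gating costs.** Test the lead at 0.05, then the other eight by Holm only if it is significant. The family-wise error stays at or below 5%. With −2 mmHg everywhere and every step evaluable, the average power of the other eight, counting studies in which the lead fails, is about 58-63% at n = 16 and 78-80% at n = 20 across the same correlations.

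**The case against.** **The study is small, acute and mechanistic, and its aim is to offer insight.** That is true, and it is why labelling the other eight as descriptive is acceptable. But the protocol itself uses the word primary and claims 5% and 80%, and those claims need an object.

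**The SAP will settle it.** It may, and it is a proper place for the fix. As written, however, section 6.2 gives an explicit rule for every test, and the SAP is described as supplementing that text.

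**37% is too high.** This stands. It assumes independence and counts false increases in PCWP, which could not support the hypothesis. The false-reduction column is the one relevant to a claim of benefit.

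Four stronger readings are tempting, and the documents do not support them:
- *The study is underpowered because 2.5 mmHg might be a per-condition SD.* Section 6.1 does not say which SD it is, but 16 is what an SD of the paired change yields, to within one participant. This calls for a clarifying phrase, no more.
- *The higher steps will fall below the required number.* Appendix 3 does stop the protocol before a rate that would exceed the age-predicted maximum (APMHR), and Appendix 4 carries this over to exercise. No ages or heart rates are given, so the loss cannot be quantified.
- *The optimal-rate hypothesis needs a powered test between rates.* Section 2.2 and the design section compare each rate only with the intrinsic rate, and no between-rate difference or SD is given from which to compute power.
- *Twenty participants are too few.* For one named comparison they are enough.

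**Conclusion.** The point holds as a matter of analysis specification and should be fixed. Nine comparisons are primary, each at two-sided 0.05, with nothing to rank or combine them, and the sample size belongs to at most one of them. Without an effect, the plan as written would produce at least one false reduction in about 6-20% of studies and at least one false positive in either direction in about 13-37%, depending on a correlation that I had to assume (0 to 0.9). The upper ends are illustrations, not estimates for this trial. These set-level figures assume paired t-tests with full numbers at every step. The single-comparison power (84.8% at 16, 92.4% at 20) rests on 2.5 mmHg being the SD of the paired change.

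**What to change.** Make these changes in sections 2.2, 6.1 and 6.2, or in the pending SAP, before PCWP results are examined. Because PCWP is seen at each visit, the cleanest time is before the first study visit; if visits have begun, state how many.

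1. Name one rate-and-workload comparison, chosen by the sponsor, as primary at two-sided 0.05.
2. Test the other eight only if it is significant, in a fixed order or by Holm. Alternatively, label them descriptive and report 95% confidence intervals.
3. In 6.1, tie the sample size to that comparison and confirm that 2.5 mmHg is the SD of the paired change. The power to state is then 84.8% at 16 and 92.4% at 20 evaluable (paired t-test).
4. Report the number evaluable at each pacing step, since the APMHR stop can remove higher rates.
5. Optional: for the hypothesis in 2.1, report paired between-rate differences within each condition with 95% confidence intervals, as estimation only.

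The cost is wording. Enrolment stays at 20, and no measurement is added. The loss is that the other eight can no longer each be claimed at an unadjusted 0.05. Under Holm behind the lead, their average power is that shown in the working, below the 84.8% and 92.4% of a single test.
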